To investigate the relationship between PK, pharmacodynamic biomarkers and anti-tumor activity	Analysis of any potential relationship between drug exposure, pharmacodynamics biomarkers and/or anti-tumor effect

To evaluate biomarkers that may predict the anti-tumor effect of CB-839 alone and in combination with nivolumab in patients with advanced/metastatic ccRCC, MEL, and NSCLC	Analysis of any potential relationship between predose biomarkers of tumor or immune state and anti-tumor effect, including PD-L1 expression in tumor
To evaluate anti-tumor effect of CB-839 as monotherapy in patients with advanced/metastatic MEL by modified RECIST 1.1 for immune-based therapeutics (iRECIST)	Assessed by ORR, DOR and PFS per iRECIST
To evaluate anti-tumor effect of CB-839 in combination with nivolumab for patients with advanced/metastatic ccRCC, MEL, and NSCLC by iRECIST	Assessed by ORR, DOR and PFS per iRECIST
To evaluate anti-tumor effect of CB-839 and nivolumab in combination after progression on CB-839 monotherapy in patients with advanced/metastatic MEL	Assessed by ORR, DOR and PFS per RECIST v1.1 and by iRECIST

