**6.6 Radiological Tumor Assessments**

All patients will be evaluated for tumor response assessed by Investigator according to both RECIST version 1.1 and modified RECIST for immune-based therapeutics (termed iRECIST) (Seymour 2017). The primary study endpoints of response rate and duration of response will be determined according to RECIST v1.1 by Investigator assessment except for Cohort 4 which will employ IRC adjudication for the primary endpoints. *In contrast to the formal study endpoints, patient management and clinical decision making during treatment should follow the principles and guidelines for iRECIST (Attachment 5).* These criteria take into account the observation that some patients with solid tumors can have an apparent radiographic flare of disease on immunotherapy that is transient and followed by radiographic disease response. If imaging shows progressive disease per RECIST v1.1 (unconfirmed PD per iRECIST), it is recommended to keep the patient on study treatment until imaging is repeated  $\geq 4$  weeks later in order to confirm PD, as described in the iRECIST recommendations (see Attachment 5). Patients who are deemed clinically unstable or are experiencing rapid progression of disease are not required to have repeat imaging for confirmation of PD. At a minimum, patients must meet the following criteria for continued treatment on study after disease progression is identified at a tumor assessment:

- Absence of symptoms and signs (including worsening of laboratory values) indicating disease progression
- No decline in ECOG performance status
- Absence of rapid progression of disease or of tumor progression at critical anatomical sites (e.g., cord compression) requiring urgent alternative medical intervention.

If repeat imaging confirms PD as described in [Attachment 5](#), patients will be discontinued from study therapy. If repeat imaging does not confirm PD, treatment with study drugs will continue and the next imaging studies will be conducted every 8 weeks as previously scheduled. In patients who discontinue study therapy early without documented disease progression, every effort should be made to continue monitoring disease status by radiologic imaging until progressive disease, death, withdrawal of consent, or initiation of new anticancer therapy.

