### 3 iRECIST Response Assessment

Overall response will also be assessed using iRECIST. Immunotherapeutics may result in infiltration of immune cells leading to transient increase in the size in malignant lesions, or undetectable lesions becoming detectable. The criteria are identical to those of RECIST 1.1 in many respects but have been adapted to account for instances where an increase in tumor burden, or the appearance of new lesions, does not reflect true tumor progression.

Key differences are described below. All responses defined using iRECIST criteria are designated with a prefix. iRECIST time-point and best overall responses will be recorded separately.

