Non-iUPD/PD	Non-iUPD/PD	Yes	iUPD	Remains iUPD unless iCPD confirmed based on ○ increase in size or number of new lesions previously identified
* Using RECIST 1.1 principles. If no PSPD occurs, RECIST 1.1 and iRECIST categories for CR, PR and SD would be the same. ** in any lesion category. *** previously identified in assessment immediately prior to this TP.				

Table S3: Time-point (TP) iResponse

All patients will have their iBOR from the start of study treatment until the end of treatment classified as outlined in Table S4.

TPR1	TPR2	TPR3	TPR4	TPR5	iBOR
iCR	iCR, iPR, iUPD, NE	iCR, iPR, iUPD, NE	iUPD	iCPD	iCR
iUPD	iPR, iSD, NE	iCR	iCR, iPR, iSD, iUPD, NE	iCR, iPR, iSD, iUPD, iCPD, NE	iCR
iUPD	iPR	iPR, iSD, iUPD, NE	iPR, iSD, iUPD, NE, iCPD	iPR, iSD, iUPD, NE, iCPD	iPR
iUPD	iSD, NE	PR	iPR, iSD, iUPD, NE	iPR, iSD, iUPD, iCPD, NE	iPR
iUPD	iSD	iSD, iUPD, NE	iSD, iUPD, iCPD, NE	iSD, iUPD, iCPD, NE	iSD
iUPD	iCPD	Anything	Anything	Anything	iCPD
iUPD	iUPD	iCPD	Anything	Anything	iCPD
iUPD	NE	NE	NE	NE	iUPD

- Table assumes a randomised study where confirmation of CR or PR is not required.
- NE = not evaluable that cycle.
- Designation "I" for BOR can be used to indicate prior iUPD to aid in data interpretation.
- For patients with non-target disease only at baseline, only CR or non-CR/non-PD can be assigned at each TPR but is not shown in the table for ease of presentation.

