## **7.7 Changes in the Conduct of the Study or Planned Analyses**

The SAP version 2.0 is amended from version 1.0 to remove restriction on the primary end point for Cohort 4 so that Cohort 4 is investigator assessed, rather than IRC assessed. That is, the primary end point for Cohort 4 is the same as the other cohorts. This decision was made by the sponsor Calithera.

SAP version 2.0 also removes references to Cohort 6 because this cohort was never enrolled.

SAP version 2.0 does not require the summarization of protocol deviations because protocol deviations may not be sufficiently standardized to allow for summarization. Though referenced in the study protocol, no iRECIST analyses are to be conducted per the SAP.

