14. Completed approximately every 8 weeks from Cycle 1 Day 1 per RECIST 1.1. Studies should include chest/abdomen/pelvis and all other known areas of disease. Evaluations may occur more frequently as clinically indicated. Patients with an objective response (CR or PR) should have repeat imaging at least 4 weeks later to confirm the objective response. In addition, patients with progressive disease should undergo a second scan at least 4 weeks later to confirm progression.
15. Cohort 4 only
16. To be included for patients with known CNS disease.
17. Archival tumor tissue must be provided from all patients on study who have archival tissue available.
18. A baseline tumor biopsy is required for all patients enrolled in Phase 2. Postdose tumor biopsies are required for all patients in Cohorts 2 and 5 and should be collected on Cycle 2 Day 1 ( $\pm$  1 week). Predose and postdose biopsies will be collected for the first 30 patients enrolled into stage 2 of Cohort 4. For all subsequently enrolled patients, only a pre-dose biopsy will be collected. Coagulation tests must be performed and evaluated within 72 to 24 hr prior to all biopsy procedures. Instructions on biopsy processing can be found in the Laboratory Manual.
19. Patients who discontinue study treatment for reason other than PD or death must continue to be followed by radiographic imaging per study schedule until PD, death, withdrawal of consent, or initiation of another cancer therapy.
20. Patients will be contacted every 3 mo for the first 12 mo then every 6 mo thereafter to confirm survival or public records may be consulted to establish survival status.

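### SAP 7.7 drops every iRECIST analysis without giving a reason, leaving one live exploratory objective of the protocol with no planned analysis

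*SAP*

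**What the plan says.** **Protocol.** Section 6.1 has an exploratory objective to evaluate the combination by iRECIST in all three tumour types, with the endpoint "Assessed by ORR, DOR and PFS per iRECIST". Section 6.6 has the investigator assess every patient under both RECIST 1.1 and iRECIST. It keeps RECIST 1.1 for the formal endpoints but says that "patient management and clinical decision making during treatment should follow the principles and guidelines for iRECIST". It recommends that a patient with RECIST 1.1 progression stay on treatment until imaging is repeated at least 4 weeks later. Unstable or rapidly progressing patients do not need the repeat scan. Attachment 5 states that "iRECIST time-point and best overall responses will be recorded separately", and the key to its scenario tables defines a separate iPD date for exploratory iRECIST analyses.

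**SAP.** Sections 5.2 and 7.4 contain RECIST 1.1 efficacy endpoints only. Appendix A, footnote 14, keeps the protocol's instruction that "patients with progressive disease should undergo a second scan at least 4 weeks later to confirm progression". Section 7.7, which lists changes to the planned analyses, says: "Though referenced in the study protocol, no iRECIST analyses are to be conducted per the SAP". Two neighbouring changes carry a reason. Cohort 6 is removed "because this cohort was never enrolled", and the deviation summary is no longer required because "protocol deviations may not be sufficiently standardized to allow for summarization". The iRECIST sentence has none.

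**The concern.** The protocol justifies treatment past RECIST 1.1 progression by the observation that an apparent flare on immunotherapy can be followed by a response. The iRECIST endpoints are the only planned summary that could show whether this happened in the trial. With them removed, the question has no planned answer. Because no reason is given, a reader of the final report cannot tell whether the data were not collected, were unusable or were simply not wanted. At stake are the completeness of reporting on a stated objective and the description of patients treated past progression. The trial's decision rules are not at stake.

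**Working it through.** There is no plan figure to reproduce. The check sets the texts side by side.

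**1. Which objectives are affected?** Three exploratory objectives in protocol 6.1 name iRECIST:
- CB-839 monotherapy in melanoma. This depends on Cohort 6, which was never enrolled, so it is moot.
- The combination after progression on monotherapy in melanoma. This also depends on Cohort 6 and is moot.
- The combination in ccRCC, melanoma and NSCLC. This does not depend on Cohort 6 and is live.

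So 3 − 2 = 1 objective, with three endpoints, is left without an analysis.

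**2. Does the RECIST 1.1 analysis cover the same ground?** No. The comparison table that opens Attachment 5 says that under RECIST 1.1 a response may not come after criteria for progression have been met. Under iRECIST it may follow unconfirmed progression (iUPD), provided progression was not confirmed. SAP Table 2 dates the PFS and DOR event at the first progression.

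**3. The protocol's own example.** Scenario B in Attachment 5 has a baseline target sum of 100, then 125 at the first time point with a new lesion, then 50, 50, 50 and 120.
- First time point: (125 − 100)/100 = +25%, above the 20% threshold, and there is a new lesion. RECIST 1.1 gives PD here and at every later time point.
- Second and third time points: (50 − 100)/100 = −50%. iRECIST gives iPR at both.
- RECIST 1.1 result: no response, PFS event at time point 1.
- iRECIST result: best response iPR, iPD date at time point 4, which is 4 − 1 = 3 assessments later.

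With the SAP as written, such a patient counts in the summaries only as a non-responder with an event at the first scan.

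**4. Where would the later response appear?** Protocol 16.1 promises listings of all data collected, so the scans would be listed. No SAP table would summarise them.

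**5. How much could one patient matter?** The number of such patients is not in the documents. As an illustration only, one patient is 100/n percentage points of iORR, with n the planned response-evaluable number in SAP Table 1. Actual numbers may differ.

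| Cohort | Stage 1 only | Both stages |
|---|---|---|
| 1 | 100/25 = 4.0 | 100/52 = 1.9 |
| 2 and 5 | 100/20 = 5.0 | 100/56 = 1.8 |
| 3 | 100/9 = 11.1 | 100/24 = 4.2 |
| 4 | Stage 1 already completed | 100/75 = 1.3 |

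**6. Is confirmation of iRECIST response settled?** The notes to Table S4 (iRECIST best overall response) say: "Table assumes a randomised study where confirmation of CR or PR is not required". This trial is not randomised. The comparison table makes iRECIST confirmation follow RECIST 1.1, which requires it in non-randomised trials. The restored analysis should therefore use confirmed iCR and iPR.

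**The case against.** The strongest reply is that this is a disclosed choice about exploratory endpoints. SAP 7.7 is the right place to announce it and does so openly. Protocol 6.6 separates iRECIST management from the formal endpoints, and protocol 16.5 describes no iRECIST method. The SAP also contains no pharmacokinetic or biomarker analysis, so leaving exploratory work out is in keeping with its scope. All of this stands and limits the weight of the point. It does not supply the missing reason. It also does not remove the difference between an objective on which a SAP is silent and one whose analysis it expressly cancels.

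A reader might infer more than the documents support:
- **That patients undergo a compulsory scan for nothing.** Footnote 14 and protocol 6.6 word the repeat scan as advice, with exemptions. Confirmation is due 4 to 8 weeks after iUPD and routine imaging is every 8 weeks, so a scheduled scan can sometimes serve. The repeat scan also informs whether treatment continues.
- **That usable iRECIST data exist for every patient.** The protocol shows that they were planned. Nothing in the documents shows how completely they were captured.
- **That 15 estimates are lost** (3 endpoints × 5 cohorts). This assumes that all five combination cohorts enrolled. The SAP says only that Cohort 6 did not.
- **That later responses vanish.** They would still be in the listings promised by protocol 16.1.

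**Conclusion.** The point holds as a gap in an exploratory analysis. SAP 7.7 leaves one live protocol objective, with its three endpoints, without a planned analysis and without an explanation. A response after unconfirmed progression would be summarised nowhere. The size of that loss is unknown. One such patient would move a cohort's iORR by between 1.3 points (Cohort 4 at 75) and 11.1 points (Cohort 3 at 9), if the planned numbers are those reached.

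A reader might also infer that the efficacy results are distorted. The documents do not support that: the primary and secondary endpoints are defined by RECIST 1.1, and dropping iRECIST changes no estimate, decision rule or error rate among them. The preferred fix assumes that the planned investigator iRECIST assessments were recorded in usable form; the fallback covers the case where they were not.

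**What to change.** Delete the iRECIST sentence in SAP 7.7 and add the following to SAP 7.4.2, labelled exploratory, for each cohort that enrolled:
- **iORR** (confirmed iCR plus iPR) on the response evaluable set, with the Clopper-Pearson 95% CI. Confirmation follows the comparison table of Attachment 5, not the assumption in the notes to Table S4.
- **iDOR** in confirmed iRECIST responders and **iPFS** on the PFS evaluable set, by Kaplan-Meier.
- **Event date and censoring.** Use the iPD date as set out in Attachment 5, including scenarios E and F, where iUPD that is never confirmed and not evaluated further still gives an iPD date. Apply the censoring rules of SAP Table 2 with iPD in place of RECIST progression.
- **A count** of patients treated past RECIST 1.1 progression, and of those with a later response.

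Use the recorded investigator iRECIST assessments. The RECIST 1.1 analyses stay as they are.

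If those data were not usably captured, state that reason in SAP 7.7, report the objective as not analysed, and still give the count and a listing of patients treated past progression.

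The cost is SAP wording and one further set of exploratory tables, with no new patients or assessments. The downside is more output that must be clearly labelled as exploratory.

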### APPENDIX A: SCHEDULE OF STUDY ASSESSMENTS

Visit	Screening	Cycle 1			Cycle 2+	End of Treatment/ Follow up
	Day -28 to -1	Day 1 (-1 day)	Days 8 and 22 ( $\pm 2$ days)	Day 15 ( $\pm 2$ days)	Days 1 and 15 ( $\pm 5$ days)	EOT: Within 28 days post treatment discontinuation
Written Informed Consent	X					
Inclusion/Exclusion Criteria	X					
Demographics and Medical History	X					
Physical Examination 	X	X	X	X	X 	X
Height	X					
Weight	X	X	X	X	X 	X
Vital Signs 	X	X	X	X	X	X
ECOG Performance Status	X	X			X 	X
12-lead ECG with QTcF 	X	X 		X 		X
Urinalysis 	X	X 	X	X	X	X
Serum Chemistry levels 	X	X 	X	X	X	X
Coagulation tests 	X	X 	X	X	X	X
Hematology 	X	X 	X	X	X	X
Serum or Urine Pregnancy Test 	X					X
Pharmacokinetic (PK) Assay 		X		X	X 	
Biomarker Assay 		X		X	X 	
Nivolumab Dosing 		X		X	X	
CB-839 Dosing 		X	X	X	X	
Baseline Radiographic Evaluation of Tumor Burden (diagnostic CT or MRI)	X 				X 	X 
MRI brain with contrast	X 				X 	
Archival Tumor Collection 	X					
Tumor Biopsy for Tumor Biomarkers 	X				X	
Adverse Events		X	X	X	X	X
Concomitant Medications	X	X	X	X	X	X
Follow up						X 

Explanation of Superscripts:

1. Complete physical exam is required at Screening and at End of Treatment. A symptom-directed physical exam can be done on all other visits. System exams are only required as clinically indicated.
2. Assessment to be completed on Day 1 of every cycle.
3. Vital sign measurements include temperature, pulse, respiratory rate and resting systolic and diastolic blood pressure. On the day of nivolumab infusion, vital signs will be obtained pre-infusion and within 30 minutes of the end of the infusion. Vital signs should be collected  $\pm$  5 minutes from the scheduled times noted above.
4. Duplicate ECGs are NOT required.
5. ECG to be performed within approximately 2 to 4 hr postdose of CB-839 administration.
6. Does not need to be repeated if the Screening sample was obtained within 3 days prior to C1D1 unless a clinically significant change is suspected.
7. Serum chemistry, coagulation, hematology and urinalysis laboratory tests should be performed and reviewed before dosing. These labs may be performed up to 48 hours prior to the planned dosing. Note that coagulation tests must be performed and reviewed within 72 to 24 hr prior to all biopsy procedures. Any new  $\geq$ Grade 3 laboratory abnormality, or change consistent with a possible irAE (as opposed to disease progression), such as liver function test elevations, electrolyte fluctuation, or hematologic deterioration should be assessed for potential risk to continue dosing. In the event of uncertainty, the medical monitor should be contacted.
8. Required of all females of child-bearing potential. Screen pregnancy test must occur within 3 days prior to C1D1.
9. Samples are collected on C1D1, C1D15, C2D1 and C3D1. See Protocol Amendment 2 [attachment 2](#) for specific time points and volume of blood collection.
10. Nivolumab dosing will take place on D1 and D15 of every cycle. On PK days (C1D1, C1D15, C2D1 and C3D1), patients will bring their morning dose of CB-839 to clinic. Pre-dose procedures must be completed, then the patient will eat breakfast and take their CB-839 dose and then the infusion of nivolumab will be administered.
11. CB-839 is given BID with food approximately 12 hours apart. On PK days (C1D1, C1D15, C2D1 and C3D1), patients will bring their morning dose of CB-839 to clinic. Pre-dose procedures must be completed, then the patient will eat breakfast and take their CB-839 dose and then the infusion of nivolumab will be administered.
12. Whenever possible, imaging should be done at the same institution/ facility and with the same modality which will be used to measure response during the patient's participation in the study. The redacted copies of the reports will be submitted and the scans must be sent to a reader for exploratory analyses. All scans from the immediate prior line of therapy will be requested for Cohorts 2, 4, and 5.
13. For Cohort 4 only: baseline radiographic imaging of disease will also occur within 7 days prior to C1D1 unless the screening assessment meets the criteria described in Protocol Amendment 2 [Section 10.1](#).
14. Completed approximately every 8 weeks from Cycle 1 Day 1 per RECIST 1.1. Studies should include chest/abdomen/pelvis and all other known areas of disease. Evaluations may occur more frequently as clinically indicated. Patients with an objective response (CR or PR) should have repeat imaging at least 4 weeks later to confirm the objective response. In addition, patients with progressive disease should undergo a second scan at least 4 weeks later to confirm progression.
15. Cohort 4 only
16. To be included for patients with known CNS disease.
17. Archival tumor tissue must be provided from all patients on study who have archival tissue available.
18. A baseline tumor biopsy is required for all patients enrolled in Phase 2. Postdose tumor biopsies are required for all patients in Cohorts 2 and 5 and should be collected on Cycle 2 Day 1 ( $\pm$  1 week). Predose and postdose biopsies will be collected for the first 30 patients enrolled into stage 2 of Cohort 4. For all subsequently enrolled patients, only a pre-dose biopsy will be collected. Coagulation tests must be performed and evaluated within 72 to 24 hr prior to all biopsy procedures. Instructions on biopsy processing can be found in the Laboratory Manual.
19. Patients who discontinue study treatment for reason other than PD or death must continue to be followed by radiographic imaging per study schedule until PD, death, withdrawal of consent, or initiation of another cancer therapy.
20. Patients will be contacted every 3 mo for the first 12 mo then every 6 mo thereafter to confirm survival or public records may be consulted to establish survival status.

